#### 7.2.2 Myocardial Infarction

The term acute MI should be used when there is acute myocardial injury with clinical evidence of acute myocardial ischemia and with detection of a rise and/or fall of cardiac troponin values with at least 1 value above the 99th percentile upper reference limit and at least 1 of the following:

- Symptoms of myocardial ischemia;
- New ischemic ECG changes;
- Development of pathological Q waves;
- Imaging evidence of new loss of viable myocardium or new regional wall motion abnormality in a pattern consistent with an ischemic etiology; or
- Identification of a coronary thrombus by angiography or autopsy (not for types 2 or 3 MI).

More details regarding the diagnosis of MI are provided in Appendix G.

#### 7.2.3 Stroke and TIA

Stroke is defined as an acute episode of focal or global neurological dysfunction caused by brain, spinal cord, or retinal vascular injury as a result of hemorrhage or infarction. A TIA, defined as a transient episode of focal neurological dysfunction caused by brain, spinal cord, or retinal ischemia without acute infarction, should not be classified as a stroke.

More details regarding the diagnosis of stroke and TIA are provided in Appendix F.

## 7.2.4 Non-Elective Coronary Revascularization

Coronary revascularization includes any coronary arterial vascular intervention done to treat clinical or functional ischemia and/or prevent major ischemic events, including PCI or surgical intervention of the coronary arteries.

A non-elective coronary revascularization includes "emergent" or "urgent" classification, as defined by the following:

• Emergency: The procedure should be performed as soon as possible because of substantial concerns that ongoing myocardial ischemia and/or MI could lead to death. "As soon as possible" refers to a participant who is of sufficient acuity that one would cancel a scheduled case to perform this procedure immediately in the next available room during business hours, or one would activate the on-call team were this to occur during off-hours; and

• Urgent: The procedure should be performed on an inpatient basis and prior to discharge because of significant concerns that there is risk of myocardial ischemia, MI, and/or death. Participants who are outpatients or in the emergency department at the time that the cardiac catheterization is requested would warrant hospital admission based on their clinical presentation.

More details regarding the classification of coronary revascularization procedures are provided in Appendix F.

## 7.2.5 Hospitalization for Unstable Angina

Unstable angina requiring hospitalization is defined as all of the following:

- Ischemic discomfort (angina or symptoms thought to be equivalent) ≥10 minutes in duration occurring either at rest or in an accelerating pattern with frequent episodes associated with progressively decreased exercise capacity;
- Prompting an unscheduled hospitalization within 24 hours of the most recent symptoms, with hospitalization being defined as an admission to an inpatient unit or a visit to an emergency department that results in at least a 24-hour stay (or a change in calendar date if the hospital admission or discharge times are not available);
- At least 1 of the following:
  - New or worsening ST or T wave changes on resting ECG (in the absence of confounders, such as left bundle branch block or left ventricular hypertrophy) (see Appendix F);
  - o Definite evidence of inducible myocardial ischemia (see Appendix F);
  - Angiographic evidence of new or worse ≥70% lesion (≥50% for left main lesion) and/or thrombus in an epicardial coronary artery that is believed to be responsible for the myocardial ischemic symptoms/signs; or
  - Need for coronary revascularization procedure (PCI or CABG) for the presumed culprit lesion(s), as defined in the bullet above. This criterion would be fulfilled if revascularization was undertaken during the unscheduled hospitalization, or subsequent to transfer to another institution without interceding home discharge.
- Negative cardiac biomarkers and no evidence of acute MI.

More details regarding the diagnosis of unstable angina are provided in Appendix F.

## 7.2.6 Hospitalization for HF

A HF hospitalization must meet all of the following criteria:

- The participant is admitted to the hospital with a primary diagnosis of HF;
- The participant's length of stay in hospital extends for at least 24 hours (or a change in calendar date if the hospital admission and discharge times are unavailable);
- The participant exhibits documented new or worsening symptoms due to HF on presentation, including at least 1 of the following symptoms: dyspnea, decreased exercise tolerance, fatigue, or other symptoms of compromised or worsened end-organ perfusion (see Appendix F);

- The participant has objective evidence of new or worsening HF, including physical examination findings and/or laboratory abnormalities (see Appendix F); and
- The participant receives at least 1 of the following treatments specifically for HF: significant augmentation in oral diuretic therapy, initiation of intravenous diuretic or vasoactive agent, or mechanical or surgical intervention.

More details regarding the diagnosis of HF are provided in Appendix F.

#### 7.3 HOMA-IR

Samples will be collected for HOMA-IR at visits specified in the Schedule of Procedures (Appendix A). Samples should be collected while the participant is fasting (a minimum of 8 hours).

## 7.4 PK Sampling

A Baseline PK sample will be collected prior to study drug administration for trough measurement of obicetrapib in plasma at visits specified in the Schedule of Procedures (Appendix A).

## 7.5 Lp(a) and ApoA1

A plasma sample for Lp(a) and ApoA1 will be collected at visits specified in the Schedule of Procedures (Appendix A). Samples should be collected prior to study drug administration and while the participant is fasting (a minimum of 8 hours).

## 7.6 Serum Archive Samples for Future Assessment

Serum archive samples will be collected at Baseline (prior to the first dose at Visit 2) and at Visit 7 (EOT) for potential future assessment of dyslipidemia and/or CV risk. Samples should be collected prior to study drug administration and while the participant is fasting (a minimum of 8 hours). Serum archive sample is not collected in China.

#### 8 SAFETY ASSESSMENTS

The safety endpoints include the following:

- Safety and tolerability profile of obicetrapib assessed by AEs, ESIs, vital signs (including blood pressure as assessed by office blood pressure measurements), ECGs, and clinical laboratory values; and
- Assessment of ABPM measured at Screening (Visit 1) and at Day 270 (Visit 6).

## 8.1 Handling of CV Events

All potential or suspected CV events will be reviewed and adjudicated by an independent CEC and reported in the appropriate clinical endpoint eCRF. In addition, these events are subject to normal AE/SAE reporting procedures.

Timelines for CV event reporting will be identical to timelines for SAE reporting (Section 8.4). All CV events occurring from the time of informed consent until the end of study participation (up to 35 days post last dose) will be reported to knowledge of the occurrence.

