#### 3 STUDY DESCRIPTION

# 3.1 Summary of Study Design

This study will be a multisite, placebo-controlled, double-blind, randomized Phase 3 study in approximately 2400 participants with underlying HeFH and/or a history of ASCVD who are not adequately controlled by their lipid-modifying therapy to evaluate the efficacy, safety, and tolerability of obicetrapib. Informed consent will be obtained from participants before the initiation of any study-specific procedures.

Approximately 2400 eligible participants will be randomized in a 2:1 ratio, respectively, to the following treatment groups:

- Obicetrapib group: One 10 mg obicetrapib tablet once daily; or
- Placebo group: 1 placebo tablet once daily.

Treatment allocation will be stratified based on CV risk (HeFH or non-HeFH) and Baseline statin dose (HIS or non-HIS). At least 70% of the participants enrolled into this study must be taking HIS. Participants with underlying HeFH but without a history of ASCVD will comprise up to a maximum of 20% of the total participants enrolled into the study. Starting on Day 1, each participant will self-administer their assigned study drug once daily until Day 365. During the Treatment Period, participants will return to the study site for efficacy and safety assessments. Blood samples for pharmacokinetic (PK) assessment will be collected at specified visits throughout the study. An onsite End of Study (EOS) Visit will be conducted 35 days after the participant's last dose of study drug, during which an assessment of vital signs, concomitant medications, CV events, and AEs will be completed and documented in the participant's record.

A subset of approximately 200 participants from selected study sites who consent to participate will be enrolled in an ambulatory blood pressure monitoring (ABPM) substudy. These participants will have a 24-hour ABPM assessment conducted at Screening (Visit 1) and Visit 6 (Day 270). In order to participate in the substudy, participants must provide written informed consent in a substudy-specific informed consent form (ICF) and must be able to provide an acceptable 24-hour ABPM data collection at Screening (Visit 1). Additional details surrounding this substudy, including the definition of an acceptable 24-hour ABPM data collection, are included in a separate study manual.

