All participants who permanently discontinue study drug should continue scheduled study visits. If the participant declines continued onsite visits but is agreeable to telephone calls, he/she will be contacted by the Investigator periodically to assess occurrence of CV events until death, documented withdrawal of participant informed consent (in writing if allowed by local regulations), or the final closure of the study.

The Investigator should show due diligence and explore all possible options to reach a participant who fails to return for a visit. In the case of participants lost to follow-up, attempts to contact the participant must be made and documented in the participant's medical records and in source documents. Per routine, in order to avoid participants lost to follow-up, the Investigator should ask the participant at the study start for the contact details of a relative or friend who can be contacted for participant contact information in case the participant cannot be reached.

Participants should not be withdrawn from follow-up unless they explicitly withdraw consent to be contacted. All efforts should therefore be made to minimize the number of participants who withdraw consent as, in general, no further information on CV events and survival status may be collected after that point. Participants who do not want regular in-person follow-up after cessation of study drug should be offered alternative methods of follow-up, including periodic telephone follow-up, contact at study closure, or assessment of health status via treating physicians or medical records. Such participants would then not be viewed as withdrawal of consent. The Investigator must explain to the participant all options for continued participation, and document which options were refused by the participant and the reason for refusal. Withdrawal of consent to all follow-up must be ascertained and documented in writing by the Investigator, who must inform the Sponsor and document the withdrawal of consent in the eCRF and medical records.

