#### 8.2 Adverse Events

An AE is defined as any untoward medical occurrence in a clinical investigation participant administered a pharmaceutical product, which does not necessarily have a causal relationship with this treatment. An AE can therefore be any unfavorable and/or unintended sign (including an abnormal laboratory finding), symptom, or disease temporally associated with the use of an investigational medicinal product, whether or not related to the investigational medicinal product. All AEs, including observed or volunteered problems, complaints, or symptoms, are to be recorded on the appropriate eCRF.

AEs, which include clinical laboratory test variables, will be monitored and documented from the time of signing of informed consent at Screening (Visit 1) until the EOS Visit (35 days after the EOT Visit). Participants should be instructed to report any AE that they experience to the Investigator, whether or not they think the event is due to study treatment. Beginning at the time of signing of informed consent, Investigators should make an assessment for AEs at each visit and record the event on the appropriate AE eCRF.

Wherever possible, a specific disease or syndrome rather than individual associated signs and symptoms should be identified by the Investigator and recorded on the eCRF. However, if an observed or reported sign or symptom is not considered a component of a specific disease or syndrome by the Investigator, it should be recorded as a separate AE on the AE eCRF. Additionally, the condition that led to a medical or surgical procedure (eg, surgery, endoscopy, tooth extraction, or transfusion) should be recorded as an AE, not the procedure itself.

Any medical condition already present at Screening (Visit 1) should be recorded as medical history and not be reported as an AE unless the medical condition or signs or symptoms present at Baseline changes in severity, frequency, or seriousness at any time during the study. In this case, it should be reported as an AE.

Clinically significant abnormal laboratory or other examination (eg, ECG) findings that are detected during the study or are present at Screening (Visit 1) and significantly worsen during the

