## 8.4 SAE Reporting – Procedures for Investigators

Initial reports
All SAEs occurring from the time of informed consent until the end of study participation (up to 35 days post last dose) will be reported, regardless of the Investigator's determination as to relatedness, to within 24 hours of the knowledge of the occurrence. After the 30-day reporting window, any SAE that the Investigator considers related to study drug must be reported to or the Sponsor/designee ( ).
To report the SAE, complete the SAE form electronically in the EDC system for the study. If the event meets serious criteria and it is not possible to access the EDC system, send an email to at a criteria are or call the SAE reporting line (telephone number listed in Section 8.7), and fax/email the completed back-up paper SAE form to contact information listed in Section 8.7) within 24 hours of awareness. When the EDC system becomes available, the SAE information must be entered within 24 hours of the system becoming available.
Follow-up reports
The Investigator must continue to follow the participant until the SAE has subsided or until the condition becomes chronic in nature, stabilizes (in the case of persistent impairment), or the participant dies.
Within 24 hours of receipt of follow-up information, the Investigator must update the SAE form electronically in the EDC system for the study and submit any supporting documentation (eg, participant discharge summary or autopsy reports) to via fax or email. If it is not possible to access the EDC system, refer to the procedures outlined above for initial reporting of SAEs.

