the following analysis will be performed. The participants who withdraw from the study before the occurrence of event or event did not occur will be censored. For these participants the time-to-event will be defined as time between Randomization and ET/EOS. Other atherosclerotic events such as AAA and carotid revascularization will be identified using the preferred terms (see [Appendix C](#)). The Clinical Events Committee (CEC) adjudicated date of event will be used to identify the first confirmed occurrence of event where appropriate, otherwise the date of event as recorded in eCRF will be used. In case when CEC cannot provide adjudicated date of death, the latest date of the last dose of study drug or date of last visit will be imputed as date of death for analysis.

The Log-rank Test

The log-rank test, stratified by CV risk (HeFH or non-HeFH), and Baseline statin therapy (HIS or non-HIS) will be used to compare differences in the time-to-event between obicetrapib and placebo.

The sample SAS code can be found below:

Note:

TREATMENT = 0 (Placebo), 1 (Obicetrapib)
CVRISK = 1 (HeFH), 2 (non-HeFH)
STATIN = 1 (HIS), 2 (non-HIS)
TIME = Time from Randomization until the first occurrence of event
CENSOR = 0 (Event occurred), 1 (Event did not occurred)

```
proc lifetest data= time_to_event method=KM  
    strata CVRISK STATIN/test=logrank group=TREATMENT;  
    time TIME*CENSOR;
```

Run;

Cox Proportional Hazard Model

A Stratified Cox proportional hazard model will be used to estimate hazard ratio between treatment groups along with the 95% confidence intervals. The model will include treatment group, CV risk (HeFH or non-HeFH), and Baseline statin therapy (HIS or non-HIS).

The Cox proportional hazard model will be implemented using SAS® Proc PHREG. The sample SAS code can be found below:

Note:

TREATMENT = 0 (Placebo), 1 (Obicetrapib)
CVRISK = 1 (HeFH), 2 (non-HeFH)
STATIN = 1 (HIS), 2 (non-HIS)
TIME = Time from Randomization until the first occurrence of event
CENSOR = 0 (Event occurred), 1 (Event did not occurred)

```
proc phreg data= time_to_event ;  
    model TIME*CENSOR=TREATMENT;  
    strata CVRISK STATIN;
```

Run;

The proportional hazard assumption will be evaluated via examination of complementary log-log (event time) versus log (time) plots. If the proportional hazard assumption raises concerns, the non-parametric Peto-Peto-Prentice test will be applied. Nominal p-values will be provided when applicable.

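### The 35-day CV-event and SAE reporting window contradicts follow-up of drug discontinuers to study closure, and the End of Study date at which the SAP censors them is undefined

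*Protocol*

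**What the plan says.** **Reporting window.** Protocol 8.1 covers "All CV events occurring from the time of informed consent until the end of study participation (up to 35 days post last dose", and 8.4 repeats the limit for SAEs: "All SAEs occurring from the time of informed consent until the end of study participation (up to 35 days post last dose". The same paragraph of 8.4 then gives a different length: "After the 30-day reporting window, any SAE that the Investigator considers related to study drug must be reported".

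**Follow-up after stopping drug.** Protocol 4.3 says: "All participants who permanently discontinue study drug should continue scheduled study visits". Those who decline onsite visits but accept telephone calls are to be "contacted by the Investigator periodically to assess occurrence of CV events until death, documented withdrawal of participant informed consent", or until the study closes. The section gives detection of CV events and vital status as the reason for continuing to the end of the study. Appendix A marks CV-event and AE assessment at every visit from V1 to V8.

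**Date of the EOS Visit.** Under Protocol 3.1 the visit "will be conducted 35 days after the participant's last dose of study drug"; the Synopsis, Appendix A and SAP 2.2.1 agree. Protocol 8.2 collects AEs "until the EOS Visit (35 days after the EOT Visit". A third route in 4.3, an ET Visit with EOS 35 days later, applies only to people who stop drug and also decline further participation.

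**Analysis.** SAP 3.4.3 says of participants without an event: "For these participants the time-to-event will be defined as time between Randomization and ET/EOS". The Poisson model for total events uses the log of each participant's follow-up time in days as its offset. SAP 3.4 makes ITT the primary efficacy population and names no other population for the time-to-event endpoints.

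**The concern.** For a participant who takes drug to Day 365 the rules agree: last dose plus 35 days and EOT plus 35 days both fall near Day 400. They separate for someone who stops early and remains in the study. Sections 8.1 and 8.4 close that person's reporting window 35 days after the last tablet, while 4.3 keeps the person under observation for CV events for the rest of the year. No section dates the EOS Visit for this person, yet the SAP uses that date to end time at risk.

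Two things are at stake. If sites resolve the conflict differently, ascertainment of CV events and SAEs after stopping drug will vary by site, which cannot be repaired at analysis. And the CV hazard ratios and rate ratios may rest on a censoring date set by when treatment stopped, or on a denominator that includes time with no duty to report events. Either could distort the comparison if discontinuation differs between arms.

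**Working it through.** The plan has no figure of its own to reproduce here: the CV endpoints are exploratory, with no event target or power statement.

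**Inputs from the documents.** N = 2400, randomized 2:1; treatment to Day 365; window of 35 days after last dose; planned follow-up for a completer 365 + 35 = 400 days.

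**Inputs assumed.** The proportion *d* who stop drug permanently but stay to Day 400, and the annual CV event rate, are not in the documents. The 5% dropout in Protocol 9.2.6 is not a drug-discontinuation rate. I use *d* = 5%, 10%, 20%, stop times uniform over 365 days, and event rates of 3% to 8% a year, the same on and off drug.

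**Step 1: one participant who stops at Day 60.**
- EOS dated from last dose: 60 + 35 = Day 95.
- EOS dated from the EOT Visit: 365 + 35 = Day 400.
- Difference: 305 days.

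**Step 2: general formula.** For a stop at Day T the window closes at T + 35, so the time outside it is 400 − (T + 35) = 365 − T days: 335 for Day 30, 281 for Day 84, 185 for Day 180, 95 for Day 270, and 0 for a completer.

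**Step 3: what the SAP does under each reading.**
- *EOS = last dose + 35.* Counted time ends with the window, so nothing unreported is analysed. The 365 − T days are discarded, and the censoring date depends on treatment, contrary to 4.3.
- *EOS near Day 400, with 8.1 and 8.4 applied literally.* The 365 − T days count as time at risk although reporting was not required.
- *EOS near Day 400, with 4.3 and Appendix A governing.* Events are captured throughout and there is no gap.

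**Step 4: share of planned follow-up affected.** The mean of 365 − T is 182.5 days. Share = *d* × 182.5 / 400; person-years = 2400 × *d* × 182.5 / 365.25.

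| *d* | Share | Person-years |
|---|---|---|
| 5% | 2.3% | 60 |
| 10% | 4.6% | 120 |
| 20% | 9.1% | 240 |

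**Step 5: events, second reading only.** Expected events = 2400 × 400 / 365.25 × rate, which is about 79 at 3% and 210 at 8%. Events outside the window = person-years × rate: from 60 × 0.03 ≈ 2 to 240 × 0.08 ≈ 19.

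**Step 6: apparent rate ratio when the true ratio is 1, second reading, all such events lost.** Ratio = (1 − *d*(obicetrapib) × 182.5/400) / (1 − *d*(placebo) × 182.5/400).
- Equal *d* in both arms: 1.00.
- 20% against 10%: 0.90875 / 0.954375 = 0.95.
- 10% against 20%: 0.954375 / 0.90875 = 1.05.

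**The case against.** The strongest reply is that this is loose wording and not a failure of capture. The operative term in 8.1 is the end of study participation, and its parenthesis simply describes a completer. Section 8.1 ties the window to SAE reporting timelines, in a sentence with text missing from the public copy, while endpoints are captured separately through the clinical endpoint eCRF and the assessment at each visit. The Clinical Events Committee adjudicates all deaths and all suspected CV events, with no time limit stated. If EOS falls near Day 400, 8.2 carries AE collection to that date.

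Much of this stands. A reader might infer that CV events are collected only to 35 days after last dose; 4.3, Appendix A and the committee's remit do not support that. A reader might also infer that the analyses do count follow-up without event capture; that requires the narrowest reading of 8.1 and 8.4 together with the latest EOS date. Bias in the mortality comparison is likewise not shown: 4.3 follows vital status, and seeks life status from public records, where local rules allow, even after full withdrawal of consent.

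The contradiction itself survives. Section 8.4 treats its window as a cutoff, since afterwards it requires only SAEs considered related to study drug, and 8.1 makes CV-event reporting timelines identical to those for SAEs. A site could follow 8.1 and 8.4 to the letter and not report an off-drug event that 4.3 is meant to find. Nor does the reply supply an EOS date. A participant followed by telephone may have no onsite EOS Visit at all, so censoring at the last CV-event assessment does more than restate the SAP's rule.

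**Conclusion.** The point holds as an inconsistency that should be corrected. The reporting window in 8.1 and 8.4, itself given two lengths in 8.4, conflicts with 4.3 and Appendix A. EOS is undefined for participants who stop drug but stay, and the SAP builds its censoring on that date.

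The size is modest and conditional. The affected share of planned follow-up is about 2% to 9% under assumed discontinuation of 5% to 20% with uniform stop times and everyone staying to Day 400; those who leave through the ET route have at most the interval between last dose and the ET Visit outside the window. A spurious effect at the null needs the literal reading with a late EOS and also unequal discontinuation; even 20% against 10% moves the ratio only to 0.95 or 1.05. With equal discontinuation it stays at 1.00, though events may be lost.

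The consequences are confined to the exploratory CV endpoints and SAE ascertainment. The primary LDL-C analysis, sample size, power and alpha are unaffected. That the CV endpoints use the ITT Population is inferred from the general statement in SAP 3.4.

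**What to change.** 1. **Protocol 8.1 and 8.4:** reconcile the window with 4.3, so that CV events and SAEs are reported to the end of each participant's study follow-up, whether or not on study drug. Remove the conflict between the 35-day and 30-day wording in 8.4.
2. **Protocol 3.1, 8.2 and Appendix A:** use one anchor for EOS. For participants who stop drug but stay, define it as the final visit after Day 365. Carry the same definition into the Synopsis, SAP 2.2.1 and SAP Table 1.
3. **SAP 3.4.3:** censor event-free participants, and end the Poisson follow-up time, at the last CV-event assessment, including telephone contacts.

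The cost is a protocol clarification and a short SAP change. Visits and telephone contacts for these participants are already planned, so the added work is mainly reporting of events found at those contacts.
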